#### Effectiveness measures

Effectiveness measures applied in the cost-effectiveness analyses correspond to the clinical endpoints in the trial. These statistical analyses are described in the clinical trial protocol.

For the EQ-5D-5L index values, central tendency and dispersion measures will be presented for both groups at baseline, 6 weeks, 3, 6, and 9 months after the inclusion in the trial. These

will be presented along with median values and the 25th and the 75th percentiles, as recommended by the EuroQoL Group.

Multivariable regression analyses will be used to estimate incremental QALYs. Because QALYs are normally left-skewed, general linear models are considered. Two models are estimated; a base-case model, adjusting for baseline utility values, and a model that, in addition, includes the variables adjusted for in the main trial. The base-case model is estimated both using missing values being imputed and using complete cases.

Baseline characteristics will be reported as percentages for binary variables and mean values and SDs for continuous variables.

### Cost-effectiveness

The economic evaluation is conducted as a within-trial analysis. The incremental cost-effectiveness ratio (ICER) between the two groups, will be calculated as the mean difference in cost between the two groups divided by the mean difference in effect.

Conventional methods to examine the sensitivity of the cost-effectiveness analysis will be applied, such as Cost-effectiveness plans using bias-corrected bootstrapping with 1000 repetitions and cost-effectiveness acceptability curves. Deterministic sensitivity analyses will be performed on the valuation of the app.

Analyses will be performed using STATA (depending on the analyser's preference).

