#### Sample size

Based on sample size and drop-out calculations (power of 90% to detect a 2-point mean group difference in RMDQ score at 3 months and a 30% drop-out rate during follow-up), the main trial aimed for 350 participants but included as many as 461 participants (ref protocol and main), with 300 of these participants from Denmark eligible for this analysis. The SELFBACK trial was powered for the clinical outcome but not the cost-effectiveness analysis.

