#### Costs

Parametric and non-parametric methods appropriate for the data will be used to report descriptive statistics (i.e., mean, standard deviation [SD], lower and upper quartiles, minimum and maximum values) for all resource variables and total costs by trial arm. Binary and categorical variables will be represented in terms of percentages.

Multivariable regression analyses will be used to estimate incremental costs. Because costs are normally right-skewed, general linear models are considered. Two models are estimated; a base-case model, adjusting only for health care costs during the 12-month pre-baseline period, and a model that in addition includes the variables adjusted for in the main trial. The base-case model is estimated both using missing values being imputed and using complete cases.

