### Missing data

Multiple imputations based on fully conditional specifications will impute missing outcome data at follow-up. For each analysis, the imputations will be based on a model that includes the outcome variables at all time points and group allocation. By multiple imputations, five imputed data sets will be created, each of which will be analysed separately. The results of the five analyses will be pooled using Rubin's rules. Table 3 shows the number of missing observations for the chosen outcome measure variables of the Danish participants (n=317).

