**Table 3. Missing data for the chosen outcome measures (n=300, Danish cohort)**

	Baseline	6 weeks	3 months	6 months	9 months
EQ5D	0	68	47	63	68
RMDQ	0	63	41	60	66
PSEQ	1	67	47	63	68

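### A minor, cheap improvement: 1,000 bootstrap repetitions leave avoidable Monte Carlo noise in the uncertainty outputs of the economic evaluation

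*SAP*

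**What the plan says.** SAP Section 4, Cost-effectiveness, defines the ICER as a ratio, "calculated as the mean difference in cost between the two groups divided by the mean difference in effect". It then says "Conventional methods to examine the sensitivity of the cost-effectiveness analysis will be applied" and gives as examples cost-effectiveness planes built with "bias-corrected bootstrapping with 1000 repetitions" and acceptability curves.

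The section gives no seed, no level for bootstrap limits and no willingness-to-pay threshold. It does not say in terms that the 1,000 draws also produce the curve, or that bias-corrected limits will be reported.

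Three other places bear on the point:

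- **Costs and Effectiveness measures:** incremental costs and QALYs come from regressions ("Because costs are normally right-skewed, general linear models are considered", with a parallel statement for QALYs). The base-case models are run on both imputed and complete-case data.
- **Missing data:** "five imputed data sets will be created, each of which will be analysed separately", with pooling by Rubin's rules. The SAP does not say how imputation and bootstrap are combined.
- **Sample size:** the analysis set is 300 Danish participants, and "The SELFBACK trial was powered for the clinical outcome but not the cost-effectiveness analysis".

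**The concern.** A bootstrap output has two kinds of uncertainty: sampling uncertainty, which it is meant to show, and Monte Carlo error from the finite number of draws, which is an artefact of computing. Bias-corrected limits suffer more from the second kind than plain percentile limits. The correction constant is estimated from the same draws and is doubled when the limits are placed.

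At stake is reproducibility. The economic analysis was not powered, so readers will lean on the plane and the curve. Probabilities of cost-effectiveness are often read to a whole percentage point, and at 1,000 repetitions such a figure can shift by a few points when the same code is rerun with another seed. With 300 participants, nothing in the plan requires so few draws.

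**Working it through.** The 1,000 is a chosen setting, so there is no figure of the plan's own to reproduce. The check is how much Monte Carlo error it implies.

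**Inputs.** B = 1,000 repetitions, bias-corrected (SAP, Cost-effectiveness); 300 participants (SAP, Sample size); m = 5 imputations (SAP, Missing data). From SAP Table 3, missing per follow-up visit is 47–68 of 300 for EQ-5D (15.7–22.7%) and 41–66 of 300 for RMDQ (13.7–22.0%). Assumed: 95% limits, a near-normal bootstrap distribution, and a between-imputation share of total variance λ of 0.10–0.30.

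**Acceptability curve.** A curve value p is a proportion of B draws, so its Monte Carlo SE is √(p(1−p)/B).

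| p | SE, B = 1,000 | 95% range | SE, B = 10,000 | 95% range |
|---|---|---|---|---|
| 0.50 | 1.58 points | ±3.1 | 0.50 | ±0.98 |
| 0.80 | 1.26 | ±2.5 | 0.40 | ±0.78 |
| 0.90 | 0.95 | ±1.9 | 0.30 | ±0.59 |
| 0.95 | 0.69 | ±1.35 | 0.22 | ±0.43 |

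Two independent runs at p = 0.50 differ by up to 1.96 × √2 × 1.58 = 4.4 points in 95% of pairs. That is a 95% range, not a maximum.

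**Bias-corrected limit**, in units of the SE of the estimate, B = 1,000:

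- Quantile noise: √(0.025 × 0.975/1,000)/0.0585 = 0.084, which is the plain percentile figure.
- Correction constant: √(0.25/1,000)/0.399 = 0.040, doubled to 0.079.
- Covariance of the two, which share draws: −2 × (0.5 × 0.025/1,000)/(0.399 × 0.0585) = −0.00107.
- Variance: 0.084² + 0.079² − 2 × 0.00107 ≈ 0.0113 (unrounded inputs), so SD ≈ 0.106 and the 95% range is ±0.21 SE. Against a half-width of 1.96 SE this is about 11%.
- At B = 10,000: 0.106/√10 = 0.034, or ±0.07 SE (about 3%).

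Simulation from a normal distribution (3,000 runs per setting) gave 0.104–0.107 and 0.034, against 0.084–0.085 and 0.027 for percentile limits.

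**Check without normality.** One invented data set of 300 people with right-skewed costs gave limit SDs of 0.096–0.109 SE at B = 1,000 and 0.028–0.034 SE at B = 10,000. A curve value near 15.7% had an SD of 1.04 points over 100 runs of 1,000 (range 12.6–18.2%) and 0.30 points over 10 runs of 10,000 (range 15.3–16.2%). Only the relative noise is used from these data.

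**Imputation noise.** The seed SD of a pooled estimate is √(λ/m) in SE units. It is combined below with the bootstrap noise of a limit as √(bootstrap² + imputation²).

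| λ | imputation, m = 5 | combined, B = 1,000 | combined, B = 10,000 | cut |
|---|---|---|---|---|
| 0.10 | 0.14 | 0.18 | 0.15 | 18% |
| 0.20 | 0.20 | 0.23 | 0.20 | 10% |
| 0.30 | 0.24 | 0.27 | 0.25 | 7% |

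Imputation noise exceeds 0.106 throughout.

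**If draws are stacked.** If the 1,000 are run in each of five imputed sets and stacked (5,000 draws), the curve range at 50% is 1.96 × √(0.25/5,000) = ±1.4 points. The gain from raising B alone is then smaller than tabulated.

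**The case against.** The strongest reply is that nothing here is wrong. One thousand repetitions is conventional, and the bootstrap is listed among example methods for showing sensitivity. The estimates themselves come from mean differences and regressions. Pooling by Rubin's rules ordinarily gives SE-based limits, so bias-corrected limits for incremental cost or effect may never be reported. The noise is also small beside sampling error: √(1 + 0.106²) = 1.0056, about half a percent extra on a limit. The ±3.1 points is the worst case at 50% and falls to ±1.35 at 95%.

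All of this stands, and it limits the point to a refinement. It gives no reason to keep the lower number where more draws cost seconds.

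Two stronger readings are tempting. A reader might infer that 10,000 repetitions would make the results practically independent of the seed. The documents do not support that for imputed effect results, because five imputations with 14–23% of EQ-5D and RMDQ values missing per follow-up visit leave a probably larger seed effect in place. It holds for complete-case results, and for costs if the register costs are complete. A reader might also infer that the change is free in every case. That is true only if imputation comes before resampling. If imputation is repeated inside each resample, imputed data sets rise from 5 × 1,000 = 5,000 to 5 × 10,000 = 50,000, and the SAP leaves the order open.

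**Conclusion.** The point holds as a minor, inexpensive improvement and not as an error. At 1,000 repetitions the bootstrap component of seed noise is up to ±3.1 points on the acceptability curve and about ±0.21 SE on any bias-corrected 95% limit. At 10,000 it is about ±1.0 points and ±0.07 SE, a √10 = 3.2-fold reduction.

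This rests on a near-normal bootstrap distribution, on 95% limits, and on the 1,000 draws feeding the curve. The last is the natural reading, but the SAP does not state it.

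It would be too strong to infer that the ICER is unstable or that a conclusion could flip. The point ICER does not use the draws, and with no willingness-to-pay threshold stated, no change of conclusion can be shown. For imputed effect results, more repetitions alone cut the combined noise by only about 7–18% (λ assumed 0.10–0.30), so the number of imputations matters at least as much.

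**What to change.** In SAP Section 4, Cost-effectiveness, replace 1,000 by at least 10,000 repetitions and record the seed. State that the draws are taken from the already imputed data sets and that they also produce the acceptability curve. State the level of any bootstrap limits, and report the Monte Carlo error of the curve.

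In Missing data, raise the number of imputations above five. With 50, for example, √(λ/m) falls to 0.045–0.077 SE. Raising both settings tenfold cuts both sources, and so their combination, by √10.

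The cost is two numbers and a sentence or two in the SAP. In the check above, 100,000 resamples of two linear regressions on 300 people took 19 seconds. So 10,000 in each of 5 imputed sets takes about 10 seconds, and 10,000 in each of 50 sets about 5 × 19 = 95 seconds. Models fitted iteratively would take longer.

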### Missing data

Multiple imputations based on fully conditional specifications will impute missing outcome data at follow-up. For each analysis, the imputations will be based on a model that includes the outcome variables at all time points and group allocation. By multiple imputations, five imputed data sets will be created, each of which will be analysed separately. The results of the five analyses will be pooled using Rubin's rules. Table 3 shows the number of missing observations for the chosen outcome measure variables of the Danish participants (n=317).

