### Settings and Participants

We recruited adults who were 18 years or older, had nonspecific LBP within the preceding 8 weeks, scored 6 points or higher on the Roland-Morris Disability Questionnaire (RMDQ) at the time of screening, had consulted a clinician (general practitioner, physiotherapist, or

chiropractor) in the region of Southern Denmark or the Trondheim municipality in Norway or had undergone a clinical examination at an outpatient spine clinic (Spine Centre of Southern Denmark) from March 8 to December 14, 2019.

A total of 461 participants were included, whereby 317 participants from Denmark and 144 from Norway. The current study is based on the data from the 300 Danish participants that provided their unique personal identification numbers, consented to the project, and further research-related use of their data beyond the RCT and are thus eligible for inclusion in this cost-effectiveness analysis. Using the personal identification numbers, data from the RCT were merged with healthcare costs and other relevant register data from Statistics Denmark and from The Danish Health Data Authority.

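### The imputation model for missing questionnaire outcomes leaves out the linked register data; the effect on the cost-QALY link is small, and incremental QALYs are biased only if non-response depends on cost differently by arm.

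*SAP*

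**What the plan says.** SAP Section 4, Missing data, plans multiple imputation by fully conditional specification for missing follow-up outcomes. On what goes into the model it is specific: "the imputations will be based on a model that includes the outcome variables at all time points and group allocation". The number of imputations is five, with pooling by Rubin's rules. No other predictor is named there or elsewhere. The paragraph leads to Table 3 ("Missing data for the chosen outcome measures"), which lists EQ-5D, RMDQ and PSEQ at five time points.

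SAP Section 3, Settings and Participants, restricts the analysis to 300 Danish participants who supplied personal identification numbers, and states that "data from the RCT were merged with healthcare costs and other relevant register data from Statistics Denmark and from The Danish Health Data Authority". Measures of resource use and costs takes primary care, hospital and prescription data from national registers. Formal productivity costs takes long-term sickness absence from the DREAM register.

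Section 4, Costs, adjusts the base-case cost model for health care cost in the 12 months before baseline. The base-case cost and QALY models are each run on imputed data and on complete cases. Uncertainty is shown by "bias-corrected bootstrapping with 1000 repetitions and cost-effectiveness acceptability curves".

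**The concern.** Register data do not depend on answering a questionnaire. When someone misses a visit, the registers should still show that person's care use, prescriptions and long sick leave over the same months. A model with only the questionnaires and arm gives the same distribution of imputed utility to a non-responder with heavy care use and one with no contacts, if their questionnaire answers agree.

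Two things are at stake:

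- **Joint distribution.** The plane and the acceptability curve rest on how costs and QALYs vary together. Imputed QALYs carry a person's own cost only as far as the questionnaire answers do.
- **Incremental QALYs.** Participants know their arm (Protocol section 2.7), so people who are doing badly may stop answering for different reasons in the two arms. If non-response follows cost differently by arm, a model without cost cannot correct for it.

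**Working it through.** The SAP states no figure for imputation bias or for the cost-QALY correlation, so there is nothing to reproduce. The amount missing comes from Table 3; the consequences come from simulation under stated assumptions.

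**Missing EQ-5D (Table 3, n=300).**
- By visit: 68, 47, 63 and 68, that is 22.7%, 15.7%, 21.0% and 22.7%.
- Overall: 68 + 47 + 63 + 68 = 246; 246 / (4 × 300) = 20.5%.
- Participants with a fully observed QALY: at most 300 − 68 = 232 and at least 300 − 246 = 54.
- The text above Table 3 gives n=317. With that denominator the rates are 21.5%, 14.8%, 19.9% and 21.5%, and nothing below changes.

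**Simulation of incremental QALYs.**
- From the SAP: visits at 0, 1.5, 3, 6 and 9 months; linear interpolation; regression of QALY on arm and baseline utility; 1:1 allocation; missingness matched to the Table 3 EQ-5D counts, at the same rate in each arm and nested across visits.
- Assumed, not in the documents: utility SD 0.20; within-person correlation 0.6; cost-utility correlation r at follow-up of −0.2 to −0.6 (half that at baseline); log-odds of non-response per SD of cost of −1, 0 or +1; utility gain 0.03 from six weeks.
- True gain: 0.03 × (0.75 − 0.0625) = 0.0206 QALY. Here 0.75 is nine months in years and 0.0625 is the baseline weight, half of 1.5/12.

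Large-sample bias (1,000,000 participants), imputing from arm and EQ-5D at all visits:

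| Non-response depends on cost | r=−0.2 | r=−0.4 | r=−0.6 |
|---|---|---|---|
| Not at all | 0.000 | 0.000 | 0.000 |
| Equally in both arms | 0.000 | 0.000 | 0.000 |
| In the app arm only | +0.003 | +0.006 | +0.009 |
| In the usual-care arm only | −0.003 | −0.006 | −0.009 |
| In opposite directions by arm | +0.006 | +0.012 | +0.019 |

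With cost added to the imputation model, bias is within 0.0002 throughout.

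At n=300, five imputations and r=−0.4, the SE is about 0.0105. Coverage of the 95% interval without cost is 0.89 (app arm only) and 0.79 (opposite directions); with cost it is 0.96 and 0.95. Complete-case bias at r=−0.4 is 0.0074 and 0.0150 in these two cases, larger than under imputation without cost (0.0060 and 0.0124).

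**Cost-QALY correlation.**
- At r=−0.4 above, the within-arm correlation falls from −0.46 to −0.40 when non-response is unrelated to cost, and to −0.38 when it is related to cost in both arms. Adding cost restores −0.46.
- A second simulation assumed no true effect, within-person correlation 0.5, cost-utility correlation −0.3 to −0.45 and about 20% missing. There it falls from −0.365 to −0.339 (unrelated) or −0.326 (cost-related).

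**Effect on the acceptability curve.** With net benefit NB = λQ − C, Var(NB) = λ²Var(Q) + Var(C) − 2λCov(Q,C). Relative sensitivity to the correlation ρ is greatest when λ·SE(Q) = SE(C); the SE is then proportional to √(1 − ρ). Holding the marginal variances fixed:
- −0.365 to −0.339: √(1.339/1.365) = 0.990, a 1.0% fall. A curve value of 0.80 becomes 0.802.
- −0.365 to −0.326: √(1.326/1.365) = 0.986, a 1.4% fall; 0.80 becomes 0.803.
- −0.46 to −0.38: √(1.38/1.46) = 0.972, a 2.8% fall; 0.80 becomes 0.807.

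**The case against.** **Costs may already be meant.** The SAP's Outcome variables heading is followed by the resource-use and productivity sections, and the cost model too is said to be run with missing values imputed. So *outcome variables* could include cost. This stands as an ambiguity. The reference to all time points and the content of Table 3 favour the questionnaire reading, and on either reading pre-baseline cost is not named.

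**The simulated model is poorer than the planned one.** It used EQ-5D and arm, without RMDQ and PSEQ, which could carry part of the cost information. This stands, so the sizes may be at the upper end. RMDQ counts are only 5, 6, 3 and 2 lower than EQ-5D counts across the four follow-ups. If largely the same people are missing, same-visit RMDQ would help few of them, but Table 3 does not show the joint pattern.

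**Stronger readings the documents do not support.**
- A reader might infer that incremental QALYs will be biased. Table 3 gives no counts by arm, and equal dependence on cost in both arms gives about zero bias.
- A reader might infer that the weaker correlation distorts the ICER. The SAP defines the ICER as a ratio of mean differences, so its point estimate does not involve the correlation.
- A reader might take the registers as the only information after a missed visit. EQ-5D missingness falls from 68 at six weeks to 47 at three months, so at least 21 participants came back, and their later answers enter the model.
- A reader might see a mismatch with the second, fully adjusted models. The SAP specifies imputed data only for the base-case models, so no mismatch is shown. The case for adding those covariates is that they are useful predictors.

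**Conclusion.** The point holds as an avoidable weakness in a specified method. On its natural reading the imputation model omits linked data that bear directly on the missing utilities. That those data continue after non-response is inferred from linkage by personal identifier; the SAP does not say so in words.

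The cost-QALY correlation is attenuated whenever cost and utility are related beyond the questionnaire answers, with or without differential drop-out. Because the correlation is negative, attenuation makes the net-benefit SE slightly too small: 1 to 1.5% in one assumed setting and 2.8% in the other. This does not amount to a materially distorted acceptability curve.

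Bias in incremental QALYs is conditional on non-response following cost differently by arm. With one arm affected it is about 0.003 to 0.009 QALY, or roughly 0.3 to 0.9 of an SE near 0.0105. Opposite dependence in the two arms, the extreme case examined, doubles it. These sizes rest on the assumed correlations and drop-out strengths; the mechanism does not. The planned complete-case analysis would not reveal or repair the problem.

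**What to change.** Amend SAP Section 4, Missing data, to specify one joint fully conditional specification for EQ-5D, RMDQ and PSEQ at all visits, in place of wording that could mean a separate model for each analysis. Add as predictors:

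- nine-month register health care cost, on a log or rank scale;
- weeks of register sickness absence;
- health care cost in the 12 months before baseline;
- the main-trial adjustment covariates listed under Patient self-reported data, which already include the clinical setting of recruitment.

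Impute separately by arm, or include arm-by-cost interactions. State explicitly whether costs count as outcome variables for this purpose.

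The cost is a revised paragraph and a few lines of code, since every variable is already planned for the linked data set. The downside is a somewhat larger imputation model and the need to transform skewed costs.

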## Section 2: Introduction

### Background and rationale

Digital health interventions (DHIs) have immense potential as accessible, personalised tools for managing health conditions. DHIs may be important for overcoming future challenges of limited resources in the healthcare sector and are part of Denmark's digital health strategy to ensure individuals' involvement in self-management of their health conditions. Despite the potential usefulness of DHIs, there is only limited research to support the claims of cost-effectiveness. The economic value of interventions is, alongside clinical efficacy, important information for decision-makers making resource allocation decisions. Consequently, there is a need to assess the health-economic impact of their use.

One example of a DHI is the SELFBACK system. Using a self-management support system delivered through an artificial intelligence-based app, persons with low back pain (LBP) were offered individually tailored self-management concordant with national and international clinical LBP guidelines. A pragmatic RCT conducted in Denmark and Norway tested the effectiveness of the SELFBACK system as an add-on to usual care showing a small but statistically significant reduction in the primary outcomes of LBP-related disability compared to usual care at 3 months. Secondary outcomes favoured the intervention also with small effect sizes, but there were sustained results for both primary and secondary outcomes at 9 months. Danish participants in the trial consented to cross-reference their information with Danish national register data. Therefore, the data available from the SELFBACK trial makes it possible to evaluate cost-effectiveness in relation to the Danish participants.

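### Five imputations are valid, but they leave the incremental QALY more dependent on the random seed than it need be; at least 20 (for example 50) would cut this at almost no cost

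*SAP*

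**What the plan says.** - **SAP, Missing data.** Missing follow-up outcomes are imputed by fully conditional specification, using the outcome at all visits plus group: "five imputed data sets will be created, each of which will be analysed separately". Then: "The results of the five analyses will be pooled using Rubin's rules". The section gives no reason for five, no seed and no target for Monte Carlo error.
- **SAP, Table 3**, headed "Missing data for the chosen outcome measures (n=300, Danish cohort": EQ-5D is missing for 0, 68, 47, 63 and 68 participants at baseline, 6 weeks, 3, 6 and 9 months. The paragraph that introduces the table gives 317, the number of all Danish participants, instead of 300.
- **SAP, Utility measure.** The 9-month QALY interpolates linearly between visits, so it draws on all five EQ-5D values.
- **SAP, Effectiveness measures.** For QALYs, "The base-case model is estimated both using missing values being imputed and using complete cases". Neither version is named as the main one.
- **SAP, Cost-effectiveness.** The ICER "will be calculated as the mean difference in cost between the two groups divided by the mean difference in effect". Its uncertainty is shown "using bias-corrected bootstrapping with 1000 repetitions and cost-effectiveness acceptability curves". How the bootstrap and the imputations combine is not stated.
- **SAP, Sample size.** "The SELFBACK trial was powered for the clinical outcome but not the cost-effectiveness analysis".
- **Protocol, section 5.2.** Multiple imputation appears only as a sensitivity analysis, without a number of imputations.

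**The concern.** With few imputations, a second analyst using the same data, model and software but another seed obtains a different pooled estimate. Rubin's rules count this noise in the interval; they do not take it out of the point estimate. The incremental QALY from the imputed data therefore carries noise that more imputations would remove, and it is the denominator of the ICER.

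This deserves attention here for two reasons. The analysis was not powered for cost-effectiveness, so the estimates will probably be imprecise. The SAP also reports of the main trial that "Secondary outcomes favoured the intervention also with small effect sizes", so the QALY difference may be small, and a fixed amount of noise is then a larger share of it. What is at stake is reproducibility: two correct runs of this plan should agree closely, and with five imputations they need not.

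**Working it through.** The documents give no Monte Carlo error or fraction of missing information (FMI), so there is no figure of the plan's own to reproduce on this point.

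**1. Amount missing (Table 3, n = 300).**
- Follow-up EQ-5D values missing: 68 + 47 + 63 + 68 = 246 of 4 × 300 = 1200, or 20.5%. On the 317 in the text: 246/1268 = 19.4%.
- Participants without a complete QALY: at least 68 (68/300 = 22.7%), if the same people miss every visit; at most 246 (82%), if nobody misses more than one.
- If visits were missed independently: 1 − (232/300)(253/300)(237/300)(232/300) = 1 − 0.398 = 60.2%. The true overlap is not reported.

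**2. FMI for the incremental QALY (assumed, by simulation).** Set-up: 300 participants, 1:1, the Table 3 EQ-5D counts, chained-equation normal imputation on all visits plus group, QALY by trapezoid, regression on group and baseline utility. Assumed: between-visit utility correlation 0.4 to 0.75, and missingness from fully nested to independent. Result: FMI 0.19-0.20 (nested), 0.11-0.14 (partly overlapping), 0.075-0.11 (independent). FMI is highest where the fewest QALYs are incomplete, because people who miss every follow-up leave only their baseline value to impute from. A second simulation, with utility SD 0.15, correlation 0.3 to 0.7 and data missing at random, gave averages of about 0.09-0.17. The range used below is 0.075 to 0.196.

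**3. Validity and efficiency at m = 5.**
- Relative efficiency = 1/(1 + FMI/m): 1/(1 + 0.075/5) = 98.5%; 1/(1 + 0.196/5) = 96.2%.
- Widening of the standard error (SE) against unlimited imputations = √(1 + FMI/m) − 1: 0.7% to 1.9%, already inside the reported interval.

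**4. Seed SD of the incremental QALY.** With B the between-imputation variance, the Monte Carlo SD is √(B/m), or about √(FMI/m) in SE units.

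| m | FMI 0.075 | FMI 0.196 |
|---|---|---|
| 5 | 0.12 | 0.20 |
| 20 | 0.06 | 0.10 |
| 50 | 0.04 | 0.06 |

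Direct simulation agrees: 0.13-0.19, 0.06-0.09 and 0.04-0.06. Two seeds can differ (95% range) by 1.96 × √2 × 0.122 = 0.34 to 1.96 × √2 × 0.198 = 0.55 SE at m = 5, and by 0.11 to 0.17 SE at m = 50. With utility SD 0.15, the second simulation puts the seed SD at about 0.0009-0.0016 QALY for m = 5, beside an SE of 0.0067-0.0084. Going from 5 to 50 cuts Monte Carlo variance tenfold whatever the FMI.

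**5. ICER denominator.** Relative seed SD = (seed SD/SE)/z, where z is the incremental QALY in SE units; relative sampling SD = 1/z.
- z = 1: seed 12-20%, sampling 100%.
- z = 2: seed 6-10%, sampling 50%.
- Even at the top of the range, √(1 + 0.20²) = 1.02, so seed noise enlarges the total by about 2%.

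**6. Acceptability curve, only if each imputed set is bootstrapped and the draws pooled.** Seed SD ≈ φ(z) × √(s × FMI/m), with φ the normal density, z here the normal quantile of the acceptability, and s the QALY share of net-benefit variance. The documents give neither a cost SD nor a willingness-to-pay threshold, so s = 0.5 is an assumption.
- At 50% acceptability: 3.5-5.6 points at m = 5, 1.7-2.8 at m = 20, 1.1-1.8 at m = 50.
- Imputations for a 1-point SD: (0.3989/0.01)² × 0.5 × FMI = 60 to 156 at 50% acceptability; (0.2434/0.01)² × 0.5 × FMI = 22 to 58 at 84%.

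**7. Imputations for 0.1 SE on the incremental QALY.** m = FMI/0.1² = 7.5 to 19.6, so 20 is enough over the assumed range.

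**The case against.** The strongest reply is that nothing here is wrong. The number of imputations is fixed in advance, the pooling rule is valid for five, and the loss of efficiency is at most about 4%. Seed noise of 0.2 SE disappears beside the sampling error, and the planned plane and curve exist to show uncertainty. The complete-case model has no seed dependence, and register costs are not touched by the imputation of follow-up outcomes. All of this stands, and it is why the point is minor. It does not show that five is a good choice when a larger number costs almost nothing.

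Four stronger readings are tempting, and the documents do not support them.
- **That five imputations bias the results or invalidate the interval.** Rubin's rules allow for the finite number.
- **That a 12-20% seed SD makes the ICER unstable.** That figure belongs to an incremental QALY 1 SE from zero, where the denominator's sampling SD is 100% and a first-order calculation is itself rough.
- **That the acceptability curve necessarily moves by several points.** The planned separate analysis of each set suggests bootstrapping within imputations, but the SAP does not say so. If imputation is done inside each bootstrap sample, the noise is averaged over 1000 repetitions and five imputations matter much less for the curve. Nor does the SAP say whether the imputed or the complete-case version feeds the ICER and the curve.
- **That 50 imputations guarantee a 1-point error on the curve.** Step 6 shows that up to 156 could be needed.

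**Conclusion.** The point holds as a minor, inexpensive gain in reproducibility. For the incremental QALY from the imputed data, five imputations leave a seed SD of about 0.12-0.20 SE, against 0.06-0.10 with 20 and 0.04-0.06 with 50. These sizes rest on an FMI of about 0.075 to 0.20, which comes from assumed utility correlations and missingness patterns; the tenfold fall in Monte Carlo variance from 5 to 50 does not. Using 317 in place of 300 would not change the conclusion. Any effect on the acceptability curve depends on an unstated order of operations. The missing statement of that order is a matter for clarification and not evidence of an error.

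**What to change.** - **SAP, Missing data.** Replace five with at least 20 imputations, for example 50. Record the seed, report the Monte Carlo error of the incremental QALY, and raise the number until that error is below a stated target such as 0.1 SE. A recorded seed makes one run repeatable but does not reduce the dependence on which seed was chosen, so it does not replace the larger number.
- **SAP, Cost-effectiveness.** As a clarification, state whether each imputed set is bootstrapped and the draws pooled, or imputation is done within each bootstrap sample, and which version of the base-case model feeds the ICER and the curve. Set the number of imputations for the curve by its own reported Monte Carlo error and not by a fixed figure.

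The cost is one or two sentences and a little computing time. In the simulated data, 50 imputations took about 0.3 seconds, and 50 within each of 1000 bootstrap samples would take 4 to 5 minutes. No new data are needed.
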